	
Definition of DLT
 
All TEAEs are relevant to the determination of DLTs unless they are clearly and solely due to the disease under study. The DLT evaluation period will be up to 91 days (7 days of APR-246 monotherapy plus 84 days for Cycle 1-3 with combination therapy) after the first dose of APR-246 is administered. A DLT is defined as any of the following TEAEs using the National Cancer Institute Common Terminology Criteria for Adverse Events (NCI-CTCAE), as follows:
 
• Any neurologic toxicity of grade 4• Any grade ≥ 3 non-hematologic toxicity except for:
• First occurrence of grade 3 electrolyte abnormalities and/or creatinine CL decrease resolving to grade 2 (or baseline if baseline is grade ≥ 2) within 48 hours with supportive treatment.• Grade 3 fatigue, nausea, vomiting, diarrhea or other manageable constitutional symptom(s) that is/are responsive to supportive therapy.• Grade 3 infection responding to appropriate antimicrobial therapy.• Any neurologic toxicity of grade 3 that does not return to grade ≤ 1 or baseline within 7 days.• Any grade ≥ 3 hematologic toxicity will be considered a DLT except for:
• Grade 3 neutropenia without fever• Grade 4 neutropenia without fever lasting 8 days or less• Grade 3 thrombocytopenia that does not result in bleeding or transfusion• Grade 3/4 lymphopenia/lymphocytosis• Grade 3/4 white blood cell (WBC) decreased• Grade 3/4 WBC increased 
Any toxicity, regardless of the NCI-CTCAE v5.0 grade, resulting in discontinuation, dose reduction or treatment with less than 75% of planned doses of APR-246 study drug, will be reviewed by the DRT, and will be considered a DLT unless clearly and solely related to the disease under study. The DRT will consist of the Medical Monitor, Site Principal Investigators, and other clinical research personnel that the Sponsor may deem appropriate.
 
G-CSF support for the management of neutropenia and prophylactic antimicrobial therapy are allowed, including during the DLT period.
 
TEAEs that meet the above criteria but that occur after the DLT evaluation period will not be defined as DLTs and will be reported as AEs/SAEs and will be reviewed across all cohorts during the study to help determine the AE profile for the respective treatment regimens under study. A patient that discontinues APR-246 therapy before completion of Cycle 3 without DLT is considered evaluable for the purpose of safety review by the DRT only if at least 75% of the scheduled doses of APR-246 were administered in Cycles 1 through 3.
 
The study will implement the following stopping criteria:
 
• Any death occurring between receipt of the first dose of APR-246 through 30 days of last dose of study treatment which is not clearly and solely due to underlying disease,• A medically equivalent SAE experienced by >1 patient, which is not clearly and solely due to underlying disease,• A severe AE (NCI-CTCAE toxicity grade >3) experienced by >2 patients that does not return to grade ≤ 1 or baseline within 7 days ,• A grade ≥ 3 neurologic AE that does not return to grade ≤ 1 or baseline within 7 days.

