5.1.4 Dose-Limiting Toxicity

All TEAEs are relevant to the determination of DLTs unless they are clearly and solely due to the disease under study. The DLT evaluation period will be up to 91 days (7 days of APR-246 monotherapy plus 84 days for Cycle 1-3 with combination therapy) after the first dose of APR-246 is administered. A DLT is defined as any of the following TEAEs using the National Cancer Institute Common Terminology Criteria for Adverse Events (NCI-CTCAE), as follows:

- Any neurologic toxicity of grade 4
- Any grade ≥ 3 non-hematologic toxicity except for:
 - First occurrence of grade 3 electrolyte abnormalities and/or creatinine CL decrease resolving to grade 2 (or baseline if baseline is grade ≥ 2) within 48 hours with supportive treatment.
 - Grade 3 fatigue, nausea, vomiting, diarrhea or other manageable constitutional symptom(s) that is/are responsive to supportive therapy.
 - Grade 3 infection responding to appropriate antimicrobial therapy.
 - Any neurologic toxicity of grade 3 that does not return to grade ≤ 1 or baseline within 7 days.
- Any grade ≥ 3 hematologic toxicity will be considered a DLT except for:
 - Grade 3 neutropenia without fever
 - Grade 4 neutropenia without fever lasting 8 days or less
 - Grade 3 thrombocytopenia that does not result in bleeding or transfusion
 - Grade 3/4 lymphopenia/lymphocytosis
 - Grade 3/4 WBC decreased
 - Grade 3/4 WBC increased

Any toxicity, regardless of the NCI-CTCAE v5.0 grade, resulting in discontinuation, dose reduction or treatment with less than 75% of planned doses of APR-246 study drug, will be reviewed by the DRT, and will be considered a DLT unless clearly and solely related to the disease under study. The DRT will consist of the Medical Monitor, Site Principal Investigators, and other clinical research personnel that the Sponsor may deem appropriate.

G-CSF support for the management of neutropenia and prophylactic antimicrobial therapy are allowed, including during the DLT period.

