Occurrence	APR-246	Venetoclax	Rituximab
1 st occurrence • Hold all study treatments until toxicity returns to baseline or grade ≤1. Treat promptly.	
Consider reducing APR-246 by one dose level from current dose for all future cycles of treatment if toxicity does not resolve to grade ≤1 within 7 days from onset date despite maximal medical intervention(s).If unable to reduce APR-246 dose, discuss with study Medical Monitor before resuming or discontinuing treatment.	Refer to Section 5.3.3.1 for venetoclax dose modification guidelines.	Resume rituximab at same dose level once event resolves to baseline or grade ≤1, except in case of serious infection. For patients diagnosed with a serious grade ≥3 infection, rituximab should be permanently discontinued.
2 nd occurrence • Hold all study treatments until toxicity returns to baseline or grade ≤1	
Consider reducing APR-246 by one dose level from starting dose for all future cycles of treatment.	Refer to Section 5.3.3.1 for venetoclax dose modification guidelines.	Reduce rituximab dose from 500 mg/m ² to 375 mg/m ² . If unable to reduce rituximab, discuss with study Medical Monitor before resuming or discontinuing rituximab. For patients diagnosed with serious grade ≥3 infection, rituximab should be permanently discontinued.
3 rd occurrence • Hold all study treatments until toxicity returns to baseline or grade ≤1. Treat promptly.	
Consult with study medical monitor to determine if further dose modifications of study treatment(s) are medically necessary or if study treatment(s) should be discontinued.		

Actions noted in table above for rituximab are specific to toxicities occurring during Cycles 2 through 7. Rituximab may be reduced by one dose level, from 500 mg/m² to 375 mg/m², when clinically indicated. Please consult with study Medical Monitor to discuss dose modification(s) for rituximab.

Treatment may be discontinued if a TEAE has not improved (to an acceptable grade) or resolved after ≥ 4 weeks, at the discretion of the Investigator. Please consult study Medical Monitor if this situation occurs.

Patients experiencing 3 occurrences of the same toxicity should be discussed with the study Medical Monitor before study treatments are resumed.

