	Grade 3	
1st occurrence: Interrupt APR-246 dosing and monitor subject; treat promptly.
 
Resume at current dose level if toxicity resolves to grade ≤ 1 or baseline, with supportive care measures, within 72 hours of onset.
 
If toxicity does not resolve to grade ≤ 1 within 72 hours despite maximal medical intervention(s), then reduce APR-246 by 1 dose level once the toxicity resolves to grade ≤ 1 or baseline.
 
If unable to reduce APR-246 dose, discuss with study Medical Monitor before resuming or discontinuing APR-246.
 
For subsequent doses of APR-246, pre-medication with prophylactic supportive therapy should be given.
 
2nd occurrence: Interrupt APR-246 dosing and monitor subject; treat promptly.
 
Reduce APR-246 by 1 dose level if the toxicity resolves to grade ≤ 1 or baseline within 72 hours of onset.
 
If toxicity does not resolve to grade ≤ 1 despite maximal medical intervention(s) within 72 hours of onset, then consult with study Medical Monitor before resuming or discontinuing APR-246.
 
If unable to reduce APR-246 dose, discuss with study Medical Monitor before resuming or discontinuing treatment.
 
Prior to subsequent doses of APR-246, reassess prophylactic supportive therapy regimen and adjust as clinically indicated.
 
3rd occurrence: Interrupt APR-246 dosing and monitor subject; treat promptly. Consult with study Medical Monitor before resuming or discontinuing APR-246.

	Grade 4	Interrupt APR-246 dosing and monitor subject; treat promptly. Consult with study Medical Monitor to discuss dose modification or permanent discontinuation of APR-246.
Any Other Toxicity	Grade 3 or 4	
Delay dose until resolution to grade ≤ 1 or baseline, then $\downarrow 1$ dose level.
 
If unable to reduce APR-246 dose, discuss with study Medical Monitor before resuming or discontinuing APR-246.

¹ Common Terminology Criteria for Adverse Events (CTCAE) version 5.

Treating physicians should use clinical judgment and may consult the Medical Monitor for additional guidance with APR-246 dose modifications.

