5.3.2.5 Management of CNS Adverse Events

If a patient reports any clinical AE of any grade during the administration period of APR-246 that could be considered to originate from the CNS (e.g., dizziness, tremor, vertigo, nausea), then the patient will be given a rescue medication as per the institutional standard of care.

Dose modifications have been successfully used to manage potential CNS effects occurring during the infusion (Table 11). For any clinical AE grade ≥ 3 , the infusion should be interrupted and if the AE resolves to CTCAE grade ≤ 1 within 2 hours, the infusion may be resumed at the same infusion rate. If

the same symptoms recur or increase in severity during re-challenge, the infusion should be interrupted.

If the event lasts longer than 2 hours, then the APR-246 infusion should be discontinued for that day and the remaining drug should be discarded.

Table 11. Management of CNS Adverse Events (e.g., Dizziness, Tremor, Confusion, and Ataxia)

Worst toxicity	Dose Modifications for APR-246
Grade 1	Maintain dose level
Grade 2	If resolved to grade ≤ 1 with medical therapy, continue same dose level If not resolved despite treatment interruption and maximal medical therapy, stop infusion and \downarrow 1 dose level for subsequent dose. If unable to reduce APR-246, discuss with study Medical Monitor before resuming or discontinuing APR-246.
Grade ≥ 3	Stop infusion and give medical therapy. If resolved (to grade ≤ 1) with medical therapy in ≤ 2 hours from onset, infusion may resume at the Investigator's discretion. If not resolved despite treatment interruption and maximal medical therapy, infusion should be discontinued for that day. \downarrow 1 dose level for subsequent dose. If unable to reduce APR-246 dose, discuss with study Medical Monitor before resuming or discontinuing APR-246.
Grade 4	Permanently discontinue patient from APR-246.

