8.4 Safety Stopping Criteria

The study will implement the following stopping criteria:

- Any death occurring between receipt of the first dose of APR-246 through 30 days of last dose of study treatment which is not clearly and solely due to underlying disease.
- A medically equivalent SAE experienced by >1 patient, which is not clearly and solely due to underlying disease.
- A severe AE (NCI-CTCAE toxicity grade >3) experienced by >2 patients that does not return to grade ≤1 or baseline within 7 days.
- A grade ≥3 neurologic AE that does not return to grade ≤1 or baseline within 7 days.

If a stopping criterion is met, enrollment will be temporarily suspended. The DRT will perform a prompt cumulative review of safety data and the circumstances of the event(s) in question to determine whether dosing and/or the protocol should be modified.

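### The DLT definition exempts grade 3 neurologic toxicity that persists and counts the kind that resolves, leaving a gap mainly at Dose Level 1

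*Combined protocol and SAP*

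**What the plan says.** Section 5.1.4 has three main DLT criteria: grade 4 neurologic toxicity, grade 3 or worse non-hematologic toxicity, and grade 3 or worse hematologic toxicity. The second opens "Any grade ≥ 3 non-hematologic toxicity except for" and lists four exceptions. Three are first grade 3 electrolyte or creatinine-clearance changes that improve within 48 hours, grade 3 constitutional symptoms that respond to supportive care, and grade 3 infections that respond to antimicrobials. The fourth is "Any neurologic toxicity of grade 3 that does not return to grade ≤ 1 or baseline within 7 days". The synopsis has the same item at the same place in the sequence, although its indentation cannot be confirmed from the extracted text.

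A catch-all follows. Toxicity of any grade "resulting in discontinuation, dose reduction or treatment with less than 75% of planned doses of APR-246 study drug" is reviewed by the Data Review Team (DRT) and counts as a DLT unless it is due to the disease alone.

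Section 8.4 lists among the events that suspend enrolment: "A grade ≥3 neurologic AE that does not return to grade ≤1 or baseline within 7 days".

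The dose-modification rules matter because they decide whether the catch-all is triggered:

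- **Table 6 (Section 5.2)**, first grade 3 or 4 non-hematologic event unresolved at 7 days: "Consider reducing APR-246 by one dose level from current dose for all future cycles of treatment if toxicity does not resolve".
- **Table 11 (Section 5.3.2.5)**, CNS events of grade 3 or worse: "If not resolved despite treatment interruption and maximal medical therapy, infusion should be discontinued for that day", with the next dose one level lower.
- **Table 10 (Section 5.3.2.4)**, any other grade 3 or 4 toxicity: hold until resolved, then go down one level.
- **Tables 10 and 11**, where no lower level is available: "If unable to reduce APR-246 dose, discuss with study Medical Monitor before resuming or discontinuing APR-246".

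**The concern.** An exception list in a DLT definition normally removes events that are short-lived or manageable. Three of these four do. The neurologic item does the reverse: it removes the event that has failed to resolve and leaves the transient one as a DLT. Taken literally, a grade 3 CNS event that settles within 2 hours, after which Table 11 lets the infusion resume, is a DLT, and one that lasts 10 days is not.

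The DLT count drives every escalation step in Section 4.1, the MTD in Section 5.1.5 and the third primary endpoint in Section 8.3.1. Neurologic toxicity is also anticipated for this drug: the protocol has CNS management rules and excludes patients at raised neurologic risk. If persistent events go uncounted, a cohort can formally clear a dose that the rule was meant to hold back. If transient events are counted against intent, escalation can stop too early.

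**Working it through.** The plan states no figure for this point. The check is of the rule's logic, followed by a sizing under assumed rates.

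**1. The same event in two rules**

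| Grade 3 neurologic event | 5.1.4 listed criteria | 8.4 |
|---|---|---|
| Resolves within 7 days | DLT | No action under the neurologic criterion |
| Does not resolve within 7 days | Exempt | One patient suspends enrolment |

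The two sections point in opposite directions.

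**2. What the catch-all recovers**

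*Discontinuation or dose reduction.* At Dose Levels 2 and 3, Tables 10 and 11 call for a one-level reduction, so many persistent events become DLTs that way. This is not assured, because Table 6 only asks that a reduction be considered and Table 10 is headed as recommendations. At Dose Level 1 (1.5 g), Table 3 lists nothing lower. Resuming at 1.5 g after the Medical Monitor discussion is neither a reduction nor a discontinuation.

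*Under 75% of doses.* Three doses per cycle over Cycles 1–3 gives 9. Missing 1, 2 or 3 leaves 8/9 = 89%, 7/9 = 78% or 6/9 = 67%, so three must be missed. Adding the lead-in IV dose (7/10 = 70%) or both lead-in doses (8/11 = 73%) still requires three.

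From Sections 4.1 and 5.1.4, with a 7-day lead-in, a 35-day Cycle 1 and 28-day cycles after that, IV doses fall on study days 1; 8, 15, 22; 43, 50, 57; and 71, 78, 85. For an event starting on a dosing day, with that infusion counted as given and visit windows ignored, the hold needed to miss the next three IV doses is:

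| Onset | Hold needed |
|---|---|
| Lead-in Day 1 | 22 − 1 = 21 days |
| Cycle 1 (day 8, 15 or 22) | 43 − 8 = 50 − 15 = 57 − 22 = 35 days |
| Cycle 2 (day 43, 50 or 57) | 71 − 43 = 78 − 50 = 85 − 57 = 28 days |
| Cycle 3 | At most 2 doses remain, so it cannot trigger |

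After Cycle 1 Day 15 the next dose is 43 − 22 = 21 days away, so an event lasting 8 to 20 days misses none.

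**3. Size**

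Assumed persistent-event rates p are 20% and 40%; other DLT types are ignored. Under the 3+3 rule the chance of two or more DLTs at one level is

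h(p) = 1 − [(1 − p)^3 + 3p(1 − p)^5]

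- h(0.20) = 1 − (0.512 + 0.197) = 0.291
- h(0.40) = 1 − (0.216 + 0.093) = 0.691

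If the catch-all recovers a share r of events, the counted rate is rp:

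| r | p = 20% | Loss | p = 40% | Loss |
|---|---|---|---|---|
| 1 | 0.291 | 0 | 0.691 | 0 |
| 0.75 | h(0.15) = 0.186 | 0.105 | h(0.30) = 0.506 | 0.185 |
| 0.5 | h(0.10) = 0.094 | 0.197 | h(0.20) = 0.291 | 0.399 |
| 0 | 0 | 0.291 | 0 | 0.691 |

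Lower event rates on top of other DLTs also matter. With other DLTs at an assumed 10%, the chance of passing a level is 1 − h(0.10) = 0.906 if exempted events are ignored. Counting them at added rates of 5%, 10% or 20% gives 0.814, 0.709 or 0.494. These gaps assume no recovery and are upper bounds.

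The 8.4 neurologic criterion would be met within the first three patients with probability 1 − 0.8^3 = 0.488 or 1 − 0.6^3 = 0.784.

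**The case against.** **The layout may mislead.** The item begins like the grade 4 neurologic criterion and comes last in its list, so it may have been meant as a separate DLT criterion that was wrongly indented. That cannot be excluded. However, the 5.1.4 list keeps its nesting for the other non-hematologic and the hematologic exceptions. As a separate criterion the item would also add nothing to the general grade 3 rule. The grade 4 item is redundant in the same way, so redundancy alone does not settle it. Under either account the text needs correcting.

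**Section 8.4 is a real backstop.** This is the strongest point. Every cohort with a persistent event is paused and reviewed by the DRT, so none of the losses above is unreviewed escalation. At Dose Level 1, two or more DLTs also lead only to a pause and DRT review under Section 4.1. But 8.4 adds nothing to the DLT count. After the review, a Dose Level 1 cohort with one uncounted event still reads 0 of 3 and qualifies to advance, where a counted event would have required three more patients.

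**The 75% calendar depends on conventions the plan does not give.** This stands. If the oral dose counts and is missed, a lead-in hold of 14 days suffices. If an aborted infusion counts as missed, holds shorten to 14 days for onset on Day 1 of Cycle 1, and Day 1 onset in Cycle 3 could reach 3 of 9. These conventions narrow the gap. They do not close it: an event after Cycle 1 Day 15 lasting 8 to 20 days would then count as one missed dose at most.

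**The rates are assumed.** They are, and zero recovery is unrealistic at Dose Levels 2 and 3. The conclusion rests on the rule's logic.

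**Conclusion.** The concern holds. As written, the listed criteria exempt persistent grade 3 neurologic toxicity, contrary to the other three exceptions in that list and to Section 8.4. The catch-all repairs much of this at Dose Levels 2 and 3. The remaining gap is mainly at Dose Level 1, where a persistent event followed by resumption at 1.5 g is not a DLT by any limb unless enough doses are missed.

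With half of the events recovered, the chance of two or more DLTs at a level falls by about 20 points at an assumed 20% rate and 40 points at 40%. The loss is zero with full recovery and at most 29 and 69 points with none. At Dose Level 1 what is lost is the rule-based bar on moving to 3.0 g/day; the judgement-based pause remains. This must be fixed, because a safety rule that governs escalation should not have to be read in reverse.

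**What to change.** In Section 5.1.4 and the synopsis, replace the bullet with: *Grade 3 neurologic toxicity that returns to grade ≤1 or baseline within 7 days.* Persistent grade 3 and all grade 4 neurologic toxicity are then DLTs at every dose level, in agreement with 8.4 and without help from the catch-all.

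This wording exempts transient grade 3 neurologic events, which the present text counts. If the sponsor wants those to remain DLTs, the bullet should be deleted from the exception list instead. Either choice makes persistent events count; the sponsor should state which was intended.

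The cost is one bullet changed in two places, with no added patients or procedures.

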administered starting at Cycle 8 for up to a total of 24 cycles. Cycle 1 will consist of 35 days. Cycles 2 and beyond will be 28 days. The safety assessment (DLT) period begins at the start of treatment and extends to the end of Cycle 3.

Patients with RT will receive APR-246 administered IV at the assigned cohort dose with standard doses of venetoclax and rituximab. Dose escalation will proceed in a standard 3 + 3 dose escalation design.

The intended three dose levels of APR-246 are: 1.5 g/day, 3.0 g/day, and 4.0 g/day administered as an IV infusion over 6 hours. The dose escalation will proceed until a pharmacologically active dose level is achieved. It will be stopped if the maximum tolerated dose (MTD) is reached at a dose level below the maximum planned dose of 4.0 g/day. For the determination of MTD the following rules will be applied:

- Three patients will be enrolled to Dose Level 1.
- If 0 patients out of 3 experience a DLT at Dose Level 1 (1.5 g/day of APR-246), the dose will advance to the next level (Dose Level 2, 3.0 g/day).
- If 1 of the first 3 patients at Dose Level 1 experiences a DLT, 3 additional patients will be recruited and treated at the same dose level (1.5 g/day of APR 246).
- If ≥ 2 patients out of 3-6 patients in a cohort experience a DLT at Dose Level 1 (1.5 g/day of APR-246), the study will temporarily discontinue enrollment and the Data Review Team (DRT) will consider further enrollment and possible dose/schedule adjustments.
- If < 2 patients out of 6 experiences a DLT at Dose Level 1 (1.5 g/day), dose escalation will proceed to the next cohort level (Dose Level 2, 3.0 g/day).
- For each cohort, if there are 0 DLTs in the first 3 patients enrolled, the cohort will advance to the next level. If there is 1 DLT in the first 3 patients enrolled to a cohort, the cohort will enroll an additional 3 patients. If there are ≥ 2 DLTs in a cohort, the prior lower dose level will be declared the MTD.
- If there are ≤ 1 DLT in the first 3 patients enrolled at Dose Level 3, 4.0 g/day APR-246, the study will enroll 3 additional patients at Dose Level 3. If there are ≤ 1 DLTs in 6 patients enrolled at Dose Level 3, 4.0 g/day APR-246 will be declared the MTD.

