6.0 STUDY EVALUATIONS

6.1 Schedule of Study Evaluations

Study evaluations are summarized in [Table 17](#) and described in Sections [6.2](#) through [6.10](#).

Table 17: Schedule of Assessments

Protocol activities	Screening ^a	APR-246 Lead-In ^b			Cycle 1				Cycles 2 -7				Cycles 8 and Beyond			Cycles 4, 7, 10, 13, 16, 19, 22 and 25 ⁱ	End of Treatment ^p	Follow-up (28 Days after End of Treatment) ^q	
		D1	D2	D3	D1	D2	D8 ^b	D15 ^b	D1 ^c	D2	D8 ^b	D15 ^b	D1 ^c	D8 ^b	D15 ^b	D1			
Informed consent	x																		
Medical history ^d	x																		
Physical examination ^e	x	x			x				x				x					x	
Height ^s	x																		
Weight	x	x			x				x				x					x	
Vital signs ^e	x	x	x		x		x	x	x	x	x	x	x	x	x	x		x	
ECOG PS	x	x			x				x				x					x	
APR-246 (IV) ^f	x				x		x	x	x	x	x	x	x	x	x	x			
APR-246 (PO) ^f		x																	
Venetoclax ^g					Ramp-up Week 1-5				Given PO at a dose of 400 mg daily through Cycle 24										
Rituximab ^h									x										
Disease assessment ⁱ	x																x	x	
Hematology ^j	x	x ^j	x ^j	x ^j	x				x	x		x	x	x	x	x		x	
Serum chemistry ^k	x	x			x			x	x		x	x	x	x	x	x		x	
Creatinine CL ^l	x																		
PD assessments ^u		x	x	x	x	x													
Blood sample for GSH assay (Local Lab) ^v		x	x	x	x														
HCV/HBV test ^t	x																		
Pregnancy test ^m	x																		
ECG ⁿ	x	x	x		x		x	x	x				x					x	
APR-246 PK sample ^o		x	x	x					x		x ^o	x ^o	x						
Clinical toxicity assessment		Starting at the time of informed consent through 30 days after last dose ^r																	
Concomitant medications		Reviewed throughout study																	
Survival																		x	

Footnotes to Schedule of Assessments

- a. All screening/baseline evaluations are performed within 28 days prior to the start of study treatment. In the event that a visit or test cannot be scheduled on the exact visit day, a window of ± 3 days is allowable. Cycle 1 is 5 weeks (35 days) in duration. Subsequent cycles are 28 days in duration.
- b. A window of ± 3 days applies to this study visit.
- c. After the first cycle, Day 1 evaluations of subsequent cycles are to be done within 3 days prior to next cycle drug administration.
- d. Full medical history is obtained at screening for safety and eligibility purposes; this will include any clinically significant findings from 28 days prior to screening date.

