6.5 Cycle 1 (Venetoclax Ramp-up, Weeks 1-5)

6.5.1 Day 1

- Physical examination: Day 1
- Weight: Day 1
- ECOG performance status ([Appendix II](#)): Day 1
- Vital signs, including blood pressure, heart rate, respiration rate and temperature
- Hematology, including complete blood count with WBC differential. Hematology test should be completed before and after APR-246 administration on Day 1
- Serum chemistry including sodium, potassium, magnesium, phosphorus, chloride, CO₂, BUN, creatinine, glucose, calcium, albumin, total protein, total bilirubin, AST, ALT, alkaline phosphatase (for TLS assessment), uric acid and LDH: Day 1
- Concomitant medications review
- Clinical toxicity assessment
- APR-246 IV administration: Day 1
- ECG before and after APR-246 administration, see [Table 19](#) (Day 1)
- Venetoclax is given PO at the dose of 20 mg during Week 1, 50 mg during Week 2, 100 mg during Week 3, 200 mg during Week 4, and 400 mg during Week 5. Each dose should be given once daily at approximately the same time every day, with a meal and water. Please see current prescribing information for venetoclax.
- *Optional* hospitalization for the first dose of 20 and 50 mg of venetoclax beginning the evening prior to the dose of venetoclax and continuing for 24 hours after, at the discretion of the treating Investigator.
- Blood samples for PD, per [Table 18](#) (Day 1)
- Blood sample for GSH assay (prior to and approximately 4 hours after APR-246 IV infusion on Day 1). Sample is collected and sent to LabCorp following sites standard practice.

6.5.2 Day 8

- Vital signs
- APR-246 IV administration
- ECG before and after APR-246 administration, see [Table 19](#)
- Venetoclax is given PO at the dose of 20 mg during Week 1, 50 mg during Week 2, 100 mg during Week 3, 200 mg during Week 4, and 400 mg during Week 5. Each dose should be given once daily at approximately the same time every day, with a meal and water. Please see current prescribing information for venetoclax.
- Clinical toxicity assessment
- Concomitant medications review

6.5.3 Day 15

- Vital signs
- APR-246 IV administration
- ECG before and after APR-246 administration, see [Table 19](#)
- Venetoclax is given PO at the dose of 20 mg during Week 1, 50 mg during Week 2, 100 mg during Week 3, 200 mg during Week 4, and 400 mg during Week 5. Each dose should be given

once daily at approximately the same time every day, with a meal and water. current prescribing information for venetoclax.

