- Hematology, including complete blood count with WBC differential
- Serum chemistry, including sodium, potassium, magnesium, phosphorus, chloride, CO₂, BUN, creatinine, glucose, calcium, albumin, total protein, total bilirubin, AST, ALT, alkaline phosphatase (for TLS assessment), uric acid and LDH
- Clinical toxicity assessment
- Concomitant medications review

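### Cycle 1 blood counts are scheduled 14 and 21 days apart with no repeat interval after grade 4 neutropenia, so the 8-day DLT threshold depends on unscheduled counts

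*Combined protocol and SAP*

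**What the plan says.** **The DLT rule.** Section 5.1.4 sets the default: "Any grade ≥ 3 hematologic toxicity will be considered a DLT except for" a list of exceptions. One is "Grade 4 neutropenia without fever lasting 8 days or less". An afebrile grade 4 episode of more than 8 days is therefore a DLT. Section 4.1 gives the period over which this applies: "The safety assessment (DLT) period begins at the start of treatment and extends to the end of Cycle 3". Under the escalation rules there, one DLT in the first three patients expands the cohort. Two or more make the level below the MTD; at Dose Level 1 they pause enrollment.

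**The scheduled counts.** In Section 6.5 the Cycle 1 Day 1 list says "Hematology test should be completed before and after APR-246 administration on Day 1". The Day 8 list has the infusion, vital signs, ECG, venetoclax, toxicity review and concomitant medications, but no hematology. The Day 15 list has "Hematology, including complete blood count with WBC differential". No later Cycle 1 visit is listed, and "Cycle 1 will consist of 35 days". In Section 6.6, Cycles 2 to 7 have counts on Days 1, 8 and 15.

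**The windows.** The footnotes to Table 17 say of the Day 8 and Day 15 columns: "A window of ± 3 days applies to this study visit". For later Day 1 visits: "After the first cycle, Day 1 evaluations of subsequent cycles are to be done within 3 days prior to next cycle drug administration".

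**General monitoring.** Sections 5.3.1 and 5.3.2.2 ask for blood counts to be followed throughout treatment but give no interval. Tables 5 and 13 hold treatment after grade 4 hematologic toxicity until counts recover. No section found states how often counts are repeated after a grade 4 result, or how the start and end of an episode are dated.

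**The concern.** The rule needs a duration with a cut at 8 days, and the scheduled Cycle 1 counts are further apart than that. Two things follow.

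- An afebrile episode long enough to be a DLT can begin and end between two scheduled counts. With no fever there may be nothing to prompt an extra draw. Such an episode drops out of the DLT count, which biases that count downward.
- An episode caught at one scheduled count has a duration that the schedule does not determine. With up to 10 centers and no stated interval or dating rule, similar episodes may be classified differently.

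Cohorts have 3 to 6 patients, so a single DLT matters. One missed DLT can turn an expansion into an escalation, or an MTD declaration into further dosing at the same level. The longer gap also covers the venetoclax steps to 200 mg and 400 mg, and Section 2.5 names neutropenia first among the drug's common adverse reactions.

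**Working it through.** The plan gives no figure for this, so there is none to reproduce. The check sets the count schedule against the 8-day cut.

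**Inputs.** Cycle 1 counts on Days 1 and 15, and Cycle 2 Day 1 = Day 36 (Sections 4.1 and 6.5). Counts on Days 1, 8 and 15 of 28-day cycles afterwards (Section 6.6). The visit lists are used because the hematology row of Table 17 could not be read reliably column by column in the text available.

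**Gaps.**
- Cycle 1: 15 − 1 = 14 days and 36 − 15 = 21 days.
- With windows: 11 to 17 days for the first. For the second, from 33 − 18 = 15 to 36 − 12 = 24 days.
- Cycles 2 and 3: 7, 7 and 14 days.

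**Chance that an episode meets no scheduled count.** Assume onset uniform over a cycle of length L and no unscheduled counts. For an episode of d days and gaps g, P(no count) = Σ max(g − d, 0) / L. The documents give no episode lengths, so a range is shown.

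| d (days) | Cycle 1, L = 35 | Cycles 2–3, L = 28 |
|---|---|---|
| 9 | (5 + 12)/35 = 49% | 5/28 = 18% |
| 11 | (3 + 10)/35 = 37% | 3/28 = 11% |
| 13 | (1 + 8)/35 = 26% | 1/28 = 4% |
| 14 | (0 + 7)/35 = 20% | 0% |
| 21 | 0% | 0% |

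Moving the Day 15 count within its window leaves the 9-day figure at 17/35, because both gaps stay above 9 days and still sum to 35. Taken 3 days early (gaps 11 and 24), it raises the 14-day figure to 10/35 = 29%.

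**What the scheduled counts show when an episode is seen.** Of 9-day episodes starting in Cycle 1, 16/35 = 46% meet exactly one count and 2/35 = 6% meet two (Cycle 2 Days 1 and 8, 7 days apart). No episode of 14 days or less gives two grade 4 scheduled counts more than 8 days apart. If only Day 15 is grade 4, its neighbors on Days 1 and 36 bracket the duration between 0 and 35 days.

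**Effect of weekly counts.** With nominal counts on Days 1, 8, 15, 22, 29 and 36, every gap is 7 days and max(7 − d, 0) = 0 for d of 9 or more, so no such episode is missed. Weekly counts still do not time 8 days: one grade 4 result between two that are not brackets 0 to 14 days.

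**Effect of the dating rule.** Suppose duration runs from the first grade 4 draw to the first draw below grade 4, with weekly detection. A true 9-day episode is detected after a delay U, uniform on 0 to 7 days, leaving 9 − U days.
- Repeats every 4 days: the recorded duration exceeds 8 only if 9 − U > 8, so U < 1, giving 1/7 = 14%.
- Repeats every 3 days: it exceeds 8 only if 9 − U > 6, so U < 3, giving 3/7 = 43%.

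Dating from first detection would therefore misclassify most true 9-day episodes as exempt.

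**The case against.** A reader might infer that the 8-day rule cannot be measured at all. The documents do not support that. Sections 5.3.1 and 5.3.2.2 call for counts throughout treatment. Tables 5 and 13 hold treatment after grade 4 toxicity until recovery, which cannot be judged without repeat counts. An episode that has been found would be followed by unscheduled counts that could help time it.

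A reader might also infer that every poorly timed episode lowers the DLT count. Only unseen ones clearly do. Section 5.1.4 makes grade 4 neutropenia a DLT unless the exception is met, so a strict reader would count an episode of unknown duration as a DLT, pushing the count up. There are other routes too. Febrile grade 4 neutropenia falls outside the exception at any duration. Toxicity that leads to APR-246 reduction, discontinuation or under 75% of planned dosing is also treated as a DLT unless wholly attributable to the disease, and Table 5 asks sites to consider a reduction when recovery takes more than 7 days.

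Nor is 49% an expected miss rate. It applies to Cycle 1 only, ignores unscheduled counts and rests on uniform onset. Cycles 2 and 3 are sampled better. Section 5.1.1 is redacted and the Pharmacy Binder is not available, so neither can be checked for count requirements.

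These points narrow the concern but do not remove it. Monitoring without an interval does not ensure a count inside a silent episode. The hold-until-recovery rule acts only after detection, cannot date onset and sets no repeat interval. The Table 5 reduction is something to consider, not a requirement.

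**Conclusion.** The point holds in limited form. Scheduled Cycle 1 counts are 14 and 21 days apart, and no repeat-count interval or dating rule follows a grade 4 result, so the 8-day threshold in Section 5.1.4 depends on unscheduled counts. With uniform onset and no unscheduled counts, 49% of 9-day and 20% of 14-day episodes in Cycle 1 meet no scheduled count, against about 18% and 0% in Cycles 2 and 3. These are upper-end illustrations.

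The downward bias is confined to afebrile episodes that go unseen. For episodes seen once the problem is inconsistent classification, in either direction. The documents give no incidence of grade 4 neutropenia, so the effect on the DLT rate or on the dose chosen cannot be calculated. It should be corrected because the DLT count drives escalation in very small cohorts and the correction is cheap.

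**What to change.** **Schedule (Section 6.5 and Table 17).** Add a complete blood count with differential at the Cycle 1 Day 8 infusion visit, and at the Day 22 and Day 29 pre-dose ramp-up draws already called for in Table 16, which now cover chemistry only. Counts become nominally weekly, and no episode of 9 days or more then falls between nominal Cycle 1 draws. The ±3-day windows can still stretch adjacent visits: Day 8 taken on Day 5 and Day 15 on Day 18 are 13 days apart.

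**Duration (Section 5.1.4).** The sponsor should state a repeat-count interval after a grade 4 count that is short enough to resolve the 8-day threshold; the choice of interval is the sponsor's. It should also state a dating rule that does not simply start at the first grade 4 draw. One option is to give the DRT the shortest duration the counts allow (first to last grade 4 draw) and the longest (last draw before to first draw after), and to apply the exception only when the counts show 8 days or less.

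**Cost and limits.** The cost is one tube at existing draws and a few local repeat counts. Repeat counts sharpen the end of an episode, not its start. With weekly detection the longest duration already includes up to 7 days before the first grade 4 draw, so the strict option would exempt few episodes unless recovery is shown within about a day or an unscheduled count narrows the onset. The sponsor should accept that caution knowingly or state in advance how brackets spanning 8 days are handled. The 14-day gap late in Cycles 2 and 3 remains and should be acknowledged.
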